## **C. Study Design**

*Overview.* There are three main stages to this experimental protocol: 1) Assessment, 2) Day 1 fMRI, and 3) Day 2 fMRI. Participants would complete these stages across 2-3 days, depending on participant need. Day 1 fMRI and Day 2 fMRI will always be consecutive days.

During the Assessment stage, participants would undergo a structured clinical interview to assess trauma history and mental health diagnoses (See Assessments Section). The assessment stage lasts 3-4 hours.

During Day 1 fMRI, participants would complete ~40 min fMRI scan, then ingest a pill (placebo, 100mg L-DOPA, or 200 mg L-DOPA) upon leaving the scanner and wait in a waiting room for ~45 minutes. Participants then complete the Side Effect Checklist to assess for any drug-related side effects. The participant would then undergo a 7 min resting-state fMRI scan, which concludes Day 1 fMRI. Day 2 fMRI lasts about 2 hours.

Participants return ~24 hours later for Day 2 fMRI, in which they first complete the Side Effect Checklist again and then complete a single ~40 minue fMRI scan. Day 2 fMRI lasts about 1 hour.

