### *Clinical Trial Procedures*

L-DOPA

*Administration.* Prior to pill ingestion, participants would undergo a standardized medical exam (see attached physician screening form) with a study physician to rule out medical and pharmacological contraindications for L-DOPA prescription. Upon passing the medical exam, the study physician would write a prescription to the UW research pharmacy, who maintains the blind, to dispense to our research staff the correct pill. Participants would be randomized to receive either a placebo, 100mg (with 25 mg carbidopa to inhibit peripheral decarboxylase), or 200mg (with 50 mg carbidopa to inhibit peripheral decarboxylase) pill of L-DOPA (see below for randomization and blinding procedures).

The study drug is prepared and maintained by the research pharmacy. Medication is put into two gel capsules, which are identical across the dose ranges of placebo, 100mg and 200mg. Medication kits are prepared separately for the three groups and stored in the locked nurses office of WisPIC along with the study logs of drug administration and allocation for each subject (e.g., subject 001, allocated to group 'blue', provided dose on 2/18/17). There is no washout period required for this study, though participants are required to have been stable on previous medications for at least 4 weeks. Use of MAO-I in past two weeks is exclusionary. As noted above, physician evaluation is performed prior to prescription being written. Participants are assessed for side-effects after 40-min and again 24-hours later.

*Justification and Rationale for L-DOPA Dose Choices.* The dose of 100 mg is consistent with prior studies of L-DOPA on learning as a dose optimizing the inverted U-shaped curve for the dopamine/performance relationship, while the dose of 200 mg is chosen as a suprathreshold dose that establishes the upper bound of the inverted U curve of the dopamine/performance relationship (Monte-Silva, Liebetanz, Grundey, Paulus, & Nitsche 2010; Thirugnanasambandam, Grundey, Paulus, & Nitsche 2011). We chose 200 mg as the suprathreshold dose, as opposed to 300 mg or 500 mg, in order to keep the dose small enough to not inadvertently break the blind (i.e., higher L-DOPA doses are more likely to result in side effects such as dizziness, nausea, fatigue, etc.), and 200 mg has been successfully used in prior learning studies as a suprathreshold dose.

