#### **D. Data and Safety Monitoring**

See separately uploaded Data and Safety Monitoring document.

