*Personal health information/Loss of confidentiality.* Standard practices will be used to protect participant confidentiality and personal health information, including removing identifiers from all data collected, using only numbers to identify participant data, and keeping all data files when not in use in a locked filing cabinet behind a locked office. No names or other identifiers will be used in computerized data files.

Furthermore, some women may participate who are currently in an abusive relationship. In cases such as this, it is sometimes possible that the abuser would become angry and retaliate against the participant for disclosing the abuse. In to protect the participant against possible retaliation from the abuser, we would assess the current safety of the participant with respect to the perpetrator. This clinical assessment would be conducted a female research staff member. Depending on participant need given their unique circumstance, an individualized safety plan would be created for the participant that might include entering therapy, withdrawing participation, entering a women's shelter, contacting the police, etc.

Participants would be notified in the informed consent that confidentiality might be breached in the case of suicidal ideation in order to protect the participant's safety.

*Side effects from acute administration of L-DOPA.* To ensure the participants protection, we escort the participant to a waiting room for monitoring for ~45 minutes after drug administration. We then administer a standardized medication Side Effect Checklist to assess for any side effects that require immediate attention. Upon return to the lab 24 hours later, we re-administer the Side Effect Checklist to assess for any new side effects that require attention prior to beginning the fMRI Day 2 procedures. Participants are additionally given a 24-hour emergency contact number in case of any study-related emergencies.

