Side effects of a single low dose of L-DOPA are minimal and might include transient dizziness, nausea, or a general feeling of discomfort. Should these side effects be observed, we would 1) remind participants that these side effects are common and short lasting, 2) tell them they can request to speak with a study's physician if they wish, 3) escort them to the UW ER if they request, or if it is clinically indicated, that they should receive immediate attention. Participants who are unable to continue with the study procedures due to side effects (e.g., not able to complete the resting-state scan 4~5 minutes after pill ingestion) would be removed from the study after following the necessary and indicated clinical procedures (e.g., escorting to ER if necessary, consulting with the study physician, referring to psychiatric treatment as indicated, etc).

**PI:** [name].

*Blood draw and genetic analysis.* To minimize any discomfort during blood draw, only study staff trained to perform blood draw will be allowed to collect the sample from the participant. To protect the identity of research participants and prevent them from being re-identified, all samples sent for analysis will be de-identified. In addition, genetic analysis will be limited to a handful of genes related to the production and movement of dopamine in the brain. This will also minimize the psychological and social risks associated with genetic analysis. Only a few genes will be tested and participants are not re-contacted on the basis of their results.

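### The 24-hour side-effect check is stated for participants generally but carried out only at the Day 2 visit, so dosed women who are removed or do not return have no scheduled check in the protocol as supplied

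*Combined protocol and SAP*

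**What the plan says.** Four places in the combined protocol and SAP bear on the later safety check.

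- Section C, Clinical Trial Procedures (L-DOPA, Administration) gives the schedule without conditions: "Participants are assessed for side-effects after 40-min and again 24-hours later".
- Section C, Study Design (Overview) ties the second check to a visit: "Participants return ~24 hours later for Day 2 fMRI, in which they first complete the Side Effect Checklist again".
- Section E, in the protections against L-DOPA side effects, does the same: "Upon return to the lab 24 hours later, we re-administer the Side Effect Checklist". Its stated purpose there is to pick up new side effects needing attention before the Day 2 procedures start.
- The continuation of that text in Section E says that women whose side effects prevent them from going on "would be removed from the study after following the necessary and indicated clinical procedures". The steps named are examples, such as a physician consultation, the emergency room or a referral.

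Other protections are stated too. On the day of dosing, "we escort the participant to a waiting room for monitoring for ~45 minutes after drug administration", and the first checklist follows. For the time outside visits, "Participants are additionally given a 24-hour emergency contact number in case of any study-related emergencies". A woman who ends imaging early because of distress is assessed by a clinical psychologist. Section D says only "See separately uploaded Data and Safety Monitoring document"; that document was not among those supplied.

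**The concern.** The general statement in Section C promises a 24-hour assessment, but the only described way of delivering it is attendance at Day 2. A woman who took the capsules and then was removed, withdrew or did not attend drops out of the schedule. One of these routes, removal, is triggered by side effects, so the women left without the second check include a group selected by the very thing it measures.

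Two things are at stake. Planned observation after dosing is otherwise short: a wait of about 45 minutes, a checklist and a 7-minute scan. The 24-hour checklist is therefore the only scheduled look at anything that lasts or arises later. And if 24-hour side effects are summarised, women who attended Day 2 would be the natural denominator, which leaves out the women removed for side effects. This point concerns safety ascertainment; the loss of Day 2 fear-response outcomes is a separate matter.

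**Working it through.** The plan gives no figure to reproduce, so the check is a reading of the passages together, followed by simple arithmetic on what an unassessed woman costs.

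**Step 1. Follow each route a dosed woman can take.**

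1. She completes Day 1 and attends Day 2. She has the checklist about 45 minutes after the dose and again at about 24 hours. Both sections agree.
2. Side effects prevent her from continuing on Day 1. The Study Design overview puts the first checklist before the resting scan, so a woman who then cannot do that scan should already have her early effects recorded. She receives the clinical steps in Section E and is removed. No 24-hour checklist is described.
3. Distress makes her stop the post-dose resting scan. She is assessed by a psychologist. Her 24-hour checklist depends on whether she returns. (Distress in the Day 2 scan does not matter here, because the checklist comes first at that visit.)
4. She does not attend Day 2, or withdraws. She has the emergency number, which depends on her calling. No 24-hour checklist is described.

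Routes 2 and 4, and route 3 if she does not return, do not deliver what the administration text states. What is lost is information on persistence and on new effects after Day 1; the early event itself should be on record.

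**Step 2. Is the loss related to side effects?** On route 2 it is, by construction. On routes 3 and 4 the documents do not say.

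**Step 3. What does one unassessed woman cost?** Let n be the women dosed in an arm, m those without a 24-hour checklist, and x those reporting effects among the n − m assessed. The rate among attenders is x/(n − m). With all dosed women as the denominator, the rate must lie between x/n and (x + m)/n, a range of width m/n. Section G plans 35 per group. Taking n = 35 as the number dosed per arm:

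- m = 1: 1/35 = 2.9 percentage points
- m = 2: 2/35 = 5.7 percentage points
- m = 3: 3/35 = 8.6 percentage points

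**Step 4. How many women might that be?** The documents give no non-return rate, so these are assumptions that show scale only:

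- 5%: 0.05 × 105 = 5.25, about 5 women (0.05 × 70 = 3.5, about 4, of the 2 × 35 = 70 on active drug)
- 10%: 0.10 × 105 = 10.5, about 11 women (7 of 70)
- 20%: 0.20 × 105 = 21 women (14 of 70)

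**The case against.** The strongest reply has four parts.

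*The follow-up may be in the document we do not have.* Section D places data and safety monitoring elsewhere, and contact with removed or absent participants could well be described there. This stands. The finding can say only that the protocol as supplied has no such contact.

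*The women are not left unprotected.* A reader might infer that those who do not return have no safety provision at all. The documents do not support that. Section E lists clinical steps with no same-day limit, a psychologist's assessment for imaging distress, and an emergency number. What is missing is a scheduled second check.

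*The plan does not show a larger loss at the higher dose.* A reader might take the sentence "higher L-DOPA doses are more likely to result in side effects such as dizziness, nausea, fatigue, etc" as the plan's own evidence that 24-hour data will be lost more often at 200 mg. That sentence explains why 200 mg was preferred to 300 mg or 500 mg in order to protect the blind. It gives no comparison of 100 mg with 200 mg and says nothing about non-return. A difference between arms is plausible and no more.

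*No 24-hour rate is planned, and effects are expected to be brief.* Section G defines no safety endpoint, so no planned estimate can be called biased. Section E calls the side effects transient, so few women may have anything to report at 24 hours, and the checklist serves partly as a screen before scanning. This stands, and it limits the weight of the point. It does not remove the mismatch: the administration text states the assessment without limiting it to women about to be scanned.

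**Conclusion.** The point holds as a gap between passages that must be reconciled. The protocol states a 24-hour side-effect assessment for participants generally, provides it only at Day 2, and removes some women before Day 2 because of side effects. Any 24-hour side-effect data gathered this way would be missing selectively for women who had side effects.

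No size can be put on the effect. The number of women affected, whether their symptoms last to 24 hours, and whether loss differs by arm are all unstated. The width of 2.9 points per woman measures what would be unknown; it is not an estimated bias, and it assumes exactly 35 women dosed per arm. The direction, understatement of 24-hour effects, follows only if women removed for side effects are more likely than attenders to have symptoms at 24 hours, which is reasonable but not documented.

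The conclusion rests on the supplied text and would fall away if the Data and Safety Monitoring document already schedules this contact. It is a modest point, worth acting on because the remedy is cheap.

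**What to change.** Reconcile the Study Design overview, the L-DOPA administration text and the two side-effect paragraphs in Section E, and check them against the Data and Safety Monitoring document, so that all say the same about who is due the 24-hour assessment. As a matter of data collection:

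- Seek the existing 24-hour Side Effect Checklist from every woman who took the capsules and has not withdrawn consent to contact, whether or not she continues in the study.
- Where Day 2 is not attended, collect it remotely. A telephone call by existing staff is one option, through a contact route agreed beforehand as safe for her, since Section E recognises the risk of retaliation by an abuser.
- Record whether each checklist was completed in person or remotely.
- Report 24-hour side effects with all dosed women as the denominator, and give the number not assessed in each arm.

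How positive answers are handled clinically is for the sponsor to decide; this point proposes no rule on it. The cost is a short contact with the women who do not return, some care in arranging it discreetly, and a possible small difference between remote and in-person answers. No new form is needed, and dosing and removal are untouched.

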## **B. Specific Aims**

**Specific Aim 1: Test the degree to which endogenous and exogenous manipulations of dopamine neurotransmission affect fear extinction learning across multiple indices.** *Hypothesis:* L-DOPA dose will interact with dopaminergic gene score to predict fear extinction learning across indices.

**Specific Aim 2: Test the degree to which post-extinction functional connectivity within dopaminergic neural networks mediates the effect of dopaminergic manipulation on fear extinction learning.** *Hypothesis:* The L-DOPA x dopaminergic gene score will predict enhanced post-extinction dopaminergic functional connectivity, which in turn predicts enhanced fear extinction recall.

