### Data analysis.

*Primary Analytic Framework for Fear Extinction Effects.* The overall data analysis framework for Aim 1 fear extinction analyses consists of a 3 (group: placebo vs 100 mg L-DOPA vs 200 mg L-DOPA) x 2 (cue: CS+ vs CS-) x 2 (context: A [learning context] vs B [extinction context]) x 6 (dopamine gene score: 0 [low endogenous dopamine] – 5 [high endogenous dopamine]) mixed design focused on Day 2 fear responding. Preliminary analyses would test for any baseline

differences in fear responding or extinction learning on Day 1 and include these variables as covariates if needed. Analyses would also control for ancestry as well as other demographic or clinical variables should they differ between groups.

*Neural circuit ROI definition and extraction.* The neural circuit indices would be 6 *a priori* regions of interest (ROI) with anatomical coordinates defined from the recent literature (Delgado et al. 2008; Haaker, Gaburro, Sah, Gartmann, Lonsdorf, Meier, Singewald, Pape, Morellini, & Kalisch 2013a; Milad, Wright, Orr, Pitman, Quirk, & Rauch 2007; Phelps, Delgado, Nearing, & LeDoux 2004; Schiller et al. 2008) and include bilateral amygdala, bilateral hippocampus, ventromedial PFC, dorsal anterior cingulate cortex. Following standard preprocessing, first-level analyses conducted for each individual separately would consist of whole-brain GLMs, in which the task design (CS+ vs CS- during Context A vs B) is modeled as boxcar events convolved with a canonical HRF. The task design is regressed onto each voxel's timecourse within a GLM framework and using restricted maximum likelihood to account for serial correlation, resulting in a whole-brain spatial map indicating the degree to which each voxel responds to CS+ vs CS- during Context A vs B. The mean contrast values for CS+ vs CS- as a function of context is then extracted from the voxels within 6 mm spherical ROIs for the six ROIs. These analyses would provide six (for each ROI) indices of activation, calculated separately for each participant, that would be used in multivariate analysis of variance (MANOVA) analyses to define the impact of L-DOPA and dopamine gene score on consolidation of fear extinction learning.

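### A woman whose side effects stop her on Day 1 is removed from the whole study, so Aim 1 loses Day 2 outcomes that could often still be collected; the likely bias in the dose contrasts is small

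*Combined protocol and SAP*

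**What the plan says.** The removal rule is in section E, under side effects from acute administration of L-DOPA. Participants who cannot go on with study procedures "due to side effects (e.g., not able to complete the resting-state scan 4~5 minutes after pill ingestion) would be removed from the study", once the necessary clinical steps have been taken. The interval printed there is probably a slip for about 45 minutes, the wait given in section C, and nothing here depends on it. The rule names no arm, and participants and staff are blinded, so it applies to placebo as well.

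The same part of section E expects little trouble: "Side effects of a single low dose of L-DOPA are minimal". If side effects occur, staff are to "remind participants that these side effects are common and short lasting". It also repeats the Side Effect Checklist at 24 hours "to assess for any new side effects that require attention prior to beginning the fMRI Day 2 procedures".

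The section C overview fixes the order of events. Participants complete a scan of about 40 minutes and "then ingest a pill (placebo, 100mg L-DOPA, or 200 mg L-DOPA) upon leaving the scanner". They wait about 45 minutes, complete the checklist and have a 7-minute resting scan, which ends Day 1. Day 2 follows about 24 hours later.

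The Aim 1 hypothesis in section B is that "L-DOPA dose will interact with dopaminergic gene score to predict fear extinction learning across indices". Section G tests it in a "mixed design focused on Day 2 fear responding". It also plans linear and quadratic contrasts across the dose groups, and preliminary analyses that look for baseline "differences in fear responding or extinction learning on Day 1 and include these variables as covariates if needed". Section G states no analysis set, no handling of missing Day 2 data, and no count of removals by arm.

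**The concern.** The rule is wider than the aims require. A missed resting scan costs Aim 2 its mediator for that woman. It costs Aim 1 nothing, because her Day 1 conditioning and extinction task is already complete and her outcome is still a day away. Removing her from the whole study discards a randomised, dosed participant for something that happened after dosing.

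If more women are removed on 200 mg than on placebo, and women prone to side effects differ in Day 2 fear, the retained groups are no longer fully comparable. The linear dose contrast could then move with no drug effect on extinction. Section C, in justifying the doses, says higher doses bring more side effects. It says so when rejecting 300 and 500 mg, however, and does not quantify 100 against 200 mg. Greater loss on L-DOPA is therefore possible but not established.

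The certain cost is simpler: Day 2 data forgone from some women in a trial of 35 per arm.

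**Working it through.** **The plan's own figure.** Section G claims power above .9 for large effects and about .8 for medium-large effects with 35 per group (N = 105). Alpha is not stated; I take 0.05 two-sided. For a one-way comparison of three groups, use the noncentral F with 2 and 102 degrees of freedom and λ = f² × 105:

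- f = 0.40: λ = 16.8, power .960.
- f = 0.30: λ = 9.45, power .779; f = 0.3125: λ = 10.25, power .814.

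The claim reproduces if medium-large means f of about 0.31.

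**Which data each aim uses.**

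| Data | When | Used by |
|---|---|---|
| Conditioning and extinction task | Day 1, before the pill | Aim 1 (baseline) |
| Resting scan | Day 1, about 45 min after the pill | Aim 2 only |
| Recall test | Day 2, about 24 h later | Aim 1 outcome; also Aim 2 |

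**Inputs that must be assumed.** The documents give neither a removal rate nor a link between side effects and outcome. I assume 3–10% removed on 200 mg (35 × 0.03 ≈ 1 to 35 × 0.10 = 3.5, so about one to four women). I assume a correlation ρ of 0.3–0.5 between proneness to side effects and the Day 2 CS+ minus CS− response.

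**Shift in the retained mean.** If the most prone fraction r of an arm is removed, the retained mean moves by ρ × φ(z_r) / (1 − r) in SD units, where z_r is the normal quantile at r and φ the normal density. Example, r = 0.10 and ρ = 0.5: 0.5 × 0.1755 / 0.90 ≈ 0.097 SD. The bias is the 200 mg value minus the placebo value. The false-positive rate is that of a two-sided 5% t test with 35(1 − r) women per arm, from the noncentral t.

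| Removed, 200 mg / placebo | Shift (SD), ρ = 0.3; 0.5 | False-positive rate, ρ = 0.3; 0.5 |
|---|---|---|
| 3% / 0% | 0.021; 0.035 | 5.1%; 5.2% |
| 5% / 0% | 0.033; 0.054 | 5.2%; 5.6% |
| 10% / 0% | 0.058; 0.097 | 5.6%; 6.8% |
| 5% / 2% | 0.018; 0.030 | 5.1%; 5.2% |
| 10% / 5% | 0.026; 0.043 | 5.1%; 5.3% |

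For scale, the standard error of a 35 v 35 difference is √(2/35) = 0.24 SD, and the difference detectable with 80% power is 0.68 SD.

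**Dose contrasts.** With removals on placebo/100/200 mg of 0/2/3%, 0/3/5%, 0/5/10% and 2/3/5%, the linear contrast (−1, 0, 1) has a false-positive rate of 5.1–6.8%. The quadratic contrast (1, −2, 1) stays at 5.0% because loss rises fairly evenly with dose. If loss occurs only at the top dose (0/0/10%, ρ = 0.5), the quadratic rate is 5.6%.

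**Day 1 adjustment.** If Day 1 responding relates to proneness as strongly as Day 2 does, adjusting for it leaves about (1 − a) of the shift, where a is the Day 1–Day 2 correlation. At a = 0.3–0.5 that is a cut of about 30–50%, leaving 0.01–0.07 SD.

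**A second bias model.** Bias = (difference in removal share) × (mean difference between removed and retained women). For 10% v 0% and a 1.0 SD difference this is 0.10 × 1.0 = 0.10 SD; for 5% v 0% and 0.5 SD it is 0.025 SD. An extreme case, 20% v 0% and 1.0 SD, gives 0.20 SD and a false-positive rate of about 12.7%.

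**Power.** At 0.68 SD, losing 1, 2, 3 or 4 women from one arm without replacement takes power from 80.0% to 79.4, 78.8, 78.1 or 77.4%.

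**Chance that the rule is used.** At least one removal in an arm of 35 has probability 1 − (1 − p)³⁵: 66% at p = 3% and 83% at p = 5%.

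**The case against.** The best reply is that this hardly matters. Every rate is assumed, the text expects minimal side effects, and 200 mg was chosen to limit them. The upper figures need 10% removed on 200 mg, none on placebo, and a correlation of 0.5. With some placebo losses the false-positive rate stays within 5.1–5.3%. The test examined is a single two-arm comparison, not the planned MANOVA with FDR, and the Aim 1 interaction hypothesis is much less exposed than the linear contrast. I accept all of this; it is why the point is minor.

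The power figures also assume that removed women are not replaced. Section C allows up to 260 to be screened to reach 105, with no replacement rule stated. With replacement, the power loss disappears and only the selection remains.

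Third, this is a safety rule for women who have just reacted to a drug, and the 24-hour checklist was written for those continuing routinely. It is not a clearance procedure. That stands in part: a woman who had to stop needs a physician's decision as well. But the example that triggers removal is one missed scan, not a serious reaction, and the safety stop on Day 1 can stay exactly as it is.

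Finally, the allocation logs and checklists would allow counts by arm, and the separate monitoring document, which was not available, may already require them. Neither would alter the removal rule or supply an analysis set.

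**Conclusion.** The concern holds as a low-priority improvement, with medium confidence. Followed as written, the rule loses Day 2 outcomes that Aim 1 could often collect, after randomisation and dosing, because of an event that affects only Aim 2 data.

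The likely bias is small: at most about 0.10 SD in the 200 mg v placebo difference under the assumed range, or about 0.4 of its standard error, and less if placebo also loses women or Day 1 responding is adjusted for. That judgement rests on removal at or below about 10% on 200 mg. It would fail if removal approached 20% and were strongly tied to outcome, which the documents give no reason to expect. No planned conclusion is shown to be at risk.

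**What to change.** 1. Amend the removal sentence in section E. A woman who cannot complete the resting scan because of side effects stops Day 1 and receives care. She is invited to Day 2 if she is well and the study physician agrees, with the existing 24-hour checklist as part of that decision.
2. Add a paragraph to section G. The Aim 1 set is all randomised women who took a pill and have Day 2 data, in their assigned arm, with or without a resting scan. The Aim 2 set is those with a usable resting scan.
3. Report by arm how many missed the resting scan, and how many lack Day 2 data, because of side effects.

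The cost is one protocol amendment, one statistical paragraph, a few counts, and Day 2 visits for perhaps one to four women in an affected arm. Each case needs a physician's decision, and the Aim 1 and Aim 2 sets will differ by a few women. Some will still not return, so the loss is reduced rather than removed.
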